In diagnostic radiology, quantitative imaging provides a layer of clinically meaningful information beyond that of qualitative interrogation. The Radiological Society of North America (RSNA) defines quantitative imaging as “the extraction of quantifiable features from medical images for the assessment of normal or the severity, degree of change, or status of a disease, injury, or chronic condition relative to normal. Quantitative imaging includes the development, standardization, and optimization of anatomical, functional, and molecular imaging acquisition protocols, data analyses, display methods, and reporting structures. These features permit the validation of accurately and precisely obtained image-derived metrics with anatomically and physiologically relevant parameters, including treatment response and outcome, and the use of such metrics in research and patient care.” ([RSNA 2018](#))

In nuclear medicine, the SUV (standard uptake value) is an established quantitative imaging metric for the assessment of disease-related activity across a variety of neurological, cardiovascular, oncological, and immunological conditions. For example, in 18F-labeled fluoro-2-deoxyglucose positron emission tomography (18F-FDG PET) imaging, SUV is used to measure the proliferative activity of malignant tumors in various cancers through the quantification of FDG uptake using the following parameters: r , the radioactivity activity concentration [kBq/mL] measured by the PET scanner within a region of interest (ROI), a' , the decay-corrected amount of injected radiolabeled FDG [kBq], and w , the weight of the patient [g], such that such that $\text{SUV} = \frac{r}{(a'/w)}$. ([Kinahan 2010](#))

Based on the clinical utility of SUV in 18F-FDG PET imaging, Navidea pursued the development of the TUV to quantify CD206 activity on planar gamma camera imaging. TUV considers the fundamental principles of SUV and introduces modifications to account for inter- and intra-patient variability and disease pathobiology. After the evaluation of several formula permutations, Navidea has established TUV as a metric for the measurement of joint-specific CD206 activity in RA through the quantification of Tc 99m tilmanocept uptake using the following parameters: \bar{x} , the decay-corrected average pixel intensity of a ROI, and B , the

decay-corrected pixel intensity of an anatomically defined area of the cerebral vasculature (serving as an intra-patient reference region), such that $TUV = \frac{\bar{X}}{B} \times 100$. Thus, the overall purpose of this study will be to test the reliability and clinical utility of TUV.

1.2 Previous Nonclinical Research and Clinical Trial Experience in Tc 99m Tilmanocept

A detailed evaluation of the nonclinical evaluations from subcutaneous (SC) and IV routes of administration, clinical pharmacokinetics (PK), clinical efficacy, and clinical safety of Tc 99m tilmanocept can be found in the accompanying Investigator's Brochure supplied by Navidea Biopharmaceuticals, Inc.

1.2.1 Nonclinical Evaluations –Subcutaneous Administration

Nonclinical studies of Tc 99m tilmanocept demonstrated that the drug selectively binds to its intended receptor (the CD206 mannose binding receptor), and is well tolerated by rats, rabbits, guinea pigs, and dogs.

PK data obtained from nonclinical studies demonstrated rapid absorption into the plasma. Urinary excretion was a major pathway of elimination. Tc 99m tilmanocept exhibited rapid clearance from the injection site, rapid uptake by the local lymph node, and low uptake by the remaining lymph nodes. Tilmanocept was well tolerated at all doses tested in nonclinical safety pharmacology studies and in single and repeated dose toxicology studies in rats, rabbits, and dogs. In some studies in rabbits and dogs, tilmanocept acted as a local irritant of the subcutis or skeletal muscle, and induced mild inflammation and tissue degeneration. The no-observed adverse-effect level (NOAEL) was 42 μ g/kg/day. Tilmanocept was not mutagenic or genotoxic in vitro or in vivo. No signs or symptoms of hypersensitivity were observed in a study in guinea pigs.

1.2.2 Nonclinical Evaluations – IV Administration

In preparation to initiate the IV route of administration, 11 preclinical tests were conducted to assess safety, toxicity, and interaction potential at doses hundreds to thousands of times the expected maximum human dose, as summarized in [Table 1](#). The nonclinical evaluations yielded safety and pharmacokinetics profiles that were appropriate for initiation of IV dosing in clinical trials. Nonclinical study results can be found in the accompanying Investigator's Brochure.

Table 1 Preclinical Tests

Type of Study / Description	Test System	Method of Administration	Dosing
Central nervous system safety pharmacology	Rat	Intravenous	37, 190, and 380 µg/animal or equivalent 490X and 61X the anticipated study doses of 50 µg and 400 µg in humans
Expanded single-dose toxicology (including toxicokinetics and local tolerance)	Rat	Intravenous	37, 190, and 380 µg/animal or equivalent 490X and 61X the anticipated study doses of 50 µg and 400 µg in humans
Respiratory Safety Pharmacology Evaluation Using Head-Out Plethysmography of Tilmanocept following Intravenous Bolus Injection in Male Rats	Rat	Intravenous	60, 120, and 300 µg/animal or equivalent 320X and 41X the anticipated study doses of 50 µg and 400 µg in humans
In Vitro Evaluation of Tilmanocept as an Inhibitor of Cytochrome P450 (CYP) Enzymes in Human Liver Microsomes	Human Liver Samples	In vitro	0.6 to 600 nM
In Vitro Evaluation of Tilmanocept as an Inhibitor of Human ABC and SLC Transporters	Human Liver Samples	In vitro	0.04, 0.4 µM
Pharmacokinetics, Excretion, and Distribution by Quantitative Whole-Body Autoradiography Following Intravenous Administration of 99mTc-Tilmanocept in Rats	Rat	Intravenous	25 µg in 0.5 mL with collection of blood, urine, feces, and carcasses for QWBA
Hemolysis and protein flocculation	Human blood samples	In vitro	2.5, 25, and 250 µg/mL whole human blood
Target profiling screen (K, Na, and Ca ion channels)	Ion Channel	In vitro	0.025 to 0.5 mg/mL

1.2.3 Clinical Pharmacokinetics (IV)

Clinical PK was evaluated in IV administered Tc 99m tilmanocept in the Phase 1 and 2 trial NAV3-21 (NCT02865434). In this trial, 12 subjects (6 RA/6 HC) were administered the maximum dose of 400 mcg tilmanocept radiolabeled with 10 mCi of Tc 99m and urine and blood data were non-compartmentally modeled to assess potential differences in drug distribution and elimination by disease group (active RA vs. HC).

Subject-level whole blood PK parameters were assessed between HC subjects (n = 6) and subjects with active RA (n = 6) to evaluate potential differences between mean maximum concentration (C_{max}), mean area under the concentration-time curve (AUC_{0-t}), mean area under the concentration-time curve extrapolated to infinity ($AUC_{0-\infty}$), mean clearance, mean half-life ($t_{1/2}$), or mean elimination rate constant (λ_z) across each disease group (Table 2). The geometric mean of whole blood clearance was 26.5 mL/min for HC subjects and 24.8 mL/min for RA patients.

Table 2 Whole Blood PK Parameter Summaries by Group

Group	Statistic	Clearance (mL/min)	$AUC(0-t)$ (min*nCi)	$AUC(0-\infty)$ (min*nCi)	C_{max} (nCi)	$T_{1/2}$ (min)
HC	n	6	6	6	6	6
	Mean	27.3	235258.0	370580.1	1244.2	759.0
	Std Dev	7.36	50010.28	92535.92	500.36	134.20
	CV%	26.9	21.3	25.0	40.2	17.7
	Geometric Mean	26.5	230853.1	360357.6	1155.5	749.3
	Lower 90% CI	21.26	193698.75	290005.04	809.55	648.36
	Upper 90% CI	33.04	275134.27	447777.17	1649.33	865.85
RA	n	6	6	6	6	6
	Mean	25.5	268110.7	396026.4	2043.8	719.1
	Std Dev	6.18	61667.51	101351.07	1211.86	138.10
	CV%	24.3	23.0	25.6	59.3	19.2
	Geometric Mean	24.8	262309.5	385984.3	1761.9	707.4
	Lower 90% CI	20.11	217187.41	315475.79	1078.28	598.97
	Upper 90% CI	30.59	316806.03	472251.44	2878.94	835.46

Similarly, subject-level urinary PK parameters including maximum rate, AUC_{0-t} , or percent recovered were assessed for HC subjects (n=6) and subjects with active RA (n=6) to evaluate potential differences between disease groups (Table 3). The geometric mean of urine percent recovered was 7.4% in HC subjects and 6.7% in RA patients.

Table 3 Urine PK Parameter Summaries by Group

Group	Statistic	Percent Recovered ^a	AUC(0-t) (h*nCi)	Max Rate (nCi/h) ^b
HC	n	6	6	6
	Mean	7.6	1468788.9	949280.7
	Std Dev	2.07	432723.27	236916.28
	CV%	27.2	29.5	25.0
	Geometric Mean	7.4	1411786.8	924858.6
	Lower 90% CI	5.84	1088888.09	752742.08
	Upper 90% CI	9.28	1830437.75	1136329.94
RA	n	6	6	6
	Mean	6.9	1384642.0	841331.0
	Std Dev	1.74	313600.65	227308.94
	CV%	25.2	22.6	27.0
	Geometric Mean	6.7	1355137.9	817282.6
	Lower 90% CI	5.46	1123310.11	659111.71
	Upper 90% CI	8.33	1634810.07	1013410.74

^a Percent recovered is the cumulative amount of radioactivity divided by the dose and multiplied by 100.

^b Maximum observed excretion rate, calculated as (radioactivity*volume)/ (end time – start time).

A comparison of the PK parameters in subjects with active RA and HC subjects does not reveal any apparent differences in the elimination of radioactivity from the body.

1.2.4 Clinical Efficacy

1.2.4.1 NAV3-23 (SC)

This was an open-label, multicenter study of Tc 99m tilmanocept by subcutaneous injection in patients with active RA and healthy controls. Tilmanocept was administered SC at 1 of 2 mass doses: [1] 50 mcg (Cohorts 1 & 3), or [2] 200 mcg (Cohorts 2 & 4). Both mass doses were radiolabeled with 2 mCi of Tc 99m. A total of 18 subjects were enrolled and evaluated (9 active RA, 9 HC). Imaging was performed 60 ± 15 minutes and 180 ± 15 minutes post injection. The following performance conclusions were drawn upon study completion:

- Based on data from this study and parallel pathology studies, Tc 99m tilmanocept localizes to activated macrophage-infiltrated joints at doses of 50 μ g and 200 μ g radiolabeled with 2.0 mCi (74.0 MBq) by SC administration.
- Across all combined RA subjects, swollen/tender joints demonstrating the highest proportions of localization include the wrists and knees.
- Based on qualitative image evaluation, Tc 99m tilmanocept does not show differences in localization between 2 to 3 and 4 to 6-hour planar imaging within dosing groups.
- Tc 99m tilmanocept demonstrates a greater frequency of localization to swollen/tender joints at 200 mcg/2.0 mCi than 50 mcg/2.0 mCi.
- There is an overall lack of concordance between qualitative observation of Tc 99m tilmanocept localization to swollen/tender joints identified in DAS28 joint count

assessment. Swollen/tender joints did not appear to be reliable predictors of presumed abnormal activated macrophage infiltration and overall disease progression when used as an isolated diagnostic system.

- Increased tilmanocept mass dosing, increased Tc 99m specific activity, and other routes of administration may enhance localization and anatomic delineation in tilmanocept-positive joints of RA patients.
- The potential for using Tc 99m tilmanocept to delineate macrophage infiltration in RA-affected joints may allow for earlier RA-specific treatment beyond the current standard of care ACR/EULAR criteria.

1.2.4.2 NAV3-21 (IV)

This was an open-label, multicenter, dose-escalation safety with PK and dosimetry study of Tc 99m tilmanocept by IV injection in HCs and subjects with active RA. Thirty-nine subjects were enrolled. A total of 27 subjects with active RA were enrolled to Groups 1 to 9 in the dose escalation phase. Group 10 consisted of 6 HCs (3 female and 3 male) and Group 11 consisted of 6 subjects with active RA (3 female and 3 male). Tilmanocept was administered IV at 1 of 3 mass doses: 50 mcg, 200 mcg, or 400 mcg. Within each mass dose group, tilmanocept was radiolabeled with 1 of 3 Tc 99m doses: 1 mCi, 5 mCi, or 10 mCi. Subjects in Groups 10 and 11 received the maximum dose of 400 mcg/10 mCi. Imaging was performed 60 ± 15 minutes and 180 ± 15 minutes p.i. Clinical efficacy conclusions for this study are still under review.

1.2.5 Clinical Safety

1.2.5.1 NAV3-23 (SC)

The NAV3-23 (NCT02683421) safety evaluation included all trial subjects injected with Tc 99m tilmanocept (N = 18). The AE monitoring was performed from the time of dose administration until completion of onsite safety assessment. There was 1 AE that was possibly related to and 1 AE that was probably related to Tc 99m tilmanocept. However, there were no AEs that led to trial discontinuation, and no SAEs were observed. There were no deaths on trial.

1.2.5.2 NAV3-21 (IV)

The primary safety endpoint of the NAV3-21 study was evaluated by examining the incidence of AEs, changes over time in clinical laboratory tests, physical exams, ECG parameters, and vital signs. The safety evaluation included all subjects who were enrolled in the study and administered Tc 99m tilmanocept (n = 39). There were no Tc 99m tilmanocept related AEs. There were no deaths during the trial; no SAEs; and no AEs that led to discontinuation from the trial.

2 STUDY OBJECTIVES

2.1 Primary Objective(s)

- To assess the longitudinal precision of TUV_{joint} and global TUV_{global} on planar imaging in subjects with clinically diagnosed active RA on stable anti-rheumatic therapy.
- To evaluate the camera-specific precision of TUV_{joint} and TUV_{global} on planar imaging in HCs and in subjects with clinically diagnosed active RA using centralized and standardized imaging parameters.
- To assess the correlation of TUV and changes in TUV with changes in clinical assessments at multiple time points after initiation of a new anti-tumor necrosis factor alpha (TNF α) biologic disease-modifying antirheumatic drug (bDMARD) therapy.

2.2 Secondary Objective(s)

- To assess the temporal post-injection stability of TUV_{joint} and TUV_{global} at a dose of 150 mcg tilmanocept radiolabeled with 10 mCi of Tc 99m.
- To establish normal ranges for TUV_{joint} in HCs.
- To assess Tc 99m tilmanocept anatomic localization based on SPECT/CT imaging of the synovial space in hands and wrists

2.3 Safety Objective(s)

- To evaluate safety through the examination of AE incidence and changes over time in laboratory tests, vital signs, and physical examination findings.

3 INVESTIGATIONAL PLAN

3.1 Overall Study Design and Plan

This is a prospective, open-label, multicenter, single and repeat-dose study designed to evaluate the reliability and sensitivity of TUV assessments in HCs and subjects with active RA. Subjects will be enrolled in 1 of 3 study arms (Table 4) with distinct timelines, study procedures, and study durations in accordance with Arm-specific eligibility requirements.

Table 4 Study Arms

Arm	Subjects	Evaluation(s)
1	HC subjects clinically free of any inflammatory disease and/or joint pain	Image Re-image
2	Subjects with clinically diagnosed active RA who have been on stable anti-rheumatic therapy	Image Re-image Test Re-test
3	Subjects with clinically diagnosed active RA who are candidates for initiation of, or change to, a new anti-TNF α bDMARD treatment.	Sensitivity Clinical Concordance

3.1.1 Arm 1: No Inflammatory and/or Joint Disease (HC Subjects)

3.1.1.1 Description of Patient Population

This arm will be comprised of HC subjects who are deemed to be clinically free of inflammatory disease(s) and/or joint pain for at least 28 days prior to the consent date. These subjects will not receive any anti-inflammatory treatment(s) (including NSAIDs) during study participation and will not have taken any such drugs at least 28 days prior to the consent date. All other concomitant medications (for non-inflammatory conditions) will have been maintained at a stable dose for at least 28 days prior to consent.

3.1.1.2 Overview of Study Procedures

Refer to [Section 7.1](#) for a detailed description of all study procedures. Refer to [Appendix 2](#) for a schedule of events and [Appendix 4](#) for a sequential diagram of study procedures.

3.1.1.3 Justification for Population

There are 2 reasons for the inclusion of this study population. The first is to evaluate the image re-image precision of TUV_{joint}. Identical image acquisitions performed up to 15 minutes apart (e.g., planar WB scan and planar bilateral hand/wrist scan followed by planar WB scan and planar bilateral hand/wrist scan 15 minutes later) will provide important information about potential differences in TUVs in the context of standardized imaging protocols. Identical image acquisitions performed 2 hours apart (e.g., planar WB scan at 60 ± 15 minutes post-drug administration and planar WB scan at 180 ± 15 minutes post-drug administration) will provide important information about any potential time-dependent pharmacokinetic effects of Tc 99m

tilmanocept on resultant TUVs. Both image re-image evaluations are ultimately designed to summarize the overall stability of TUV.

The second reason is to establish normal ranges for TUV_{joint}. By determining the upper limit of normal (ULN) for average TUV_{joint} across pooled joints (e.g., MCPs 1-5) across patients, these assessments can be further investigated for their utility in providing clinically meaningful reference data for symptomatic individuals presenting to the clinic.

3.1.2 Arm 2: Stable Anti-Rheumatic Therapy (RA Subjects)

3.1.2.1 Description of Patient Population

This arm will be comprised of subjects with clinically diagnosed active RA on stable anti-inflammatory and/or anti-rheumatic therapy. All subjects' RA diagnoses will be moderate to severe in accordance with a 2010 ACR/EULAR score of 6 or higher. All subjects receiving traditional DMARDs must have been on therapy for ≥ 90 days and at a stable dose for ≥ 30 days prior to the first imaging visit; all subjects receiving bDMARDs or JAK inhibitors must have been on stable therapy for at least 180 days prior to the first imaging visit; and all subjects receiving NSAIDs and/or oral corticosteroids must have been on therapy for at least 28 days prior to the first imaging visit.

3.1.2.2 Overview of Study Procedures

Subjects in this arm will have a total of 3 on-site visits and 2 telephone safety assessments. The maximum possible study duration for these subjects will be 42 days.

Refer to [Section 7.1](#) for a detailed description of all study procedures. Refer to [Appendix 2](#) for a schedule of events and [Appendix 4](#) for a sequential diagram of study procedures.

Justification for Population

There are 2 reasons for the inclusion of this study population. The first is to evaluate the image re-image precision of TUV_{joint} and TUV_{global}. Identical image acquisitions performed up to 15 minutes apart (e.g., planar WB scan and planar bilateral hand/wrist scan followed by planar WB scan and planar bilateral hand/wrist scan 15 minutes later) will provide important information about potential differences in TUVs in the context of standardized imaging protocols. Identical image acquisitions performed 2 hours apart (e.g., planar WB scan at 60 ± 15 minutes post-drug administration and planar WB scan at 180 ± 15 minutes post-drug administration) will provide important information about any potential time-dependent pharmacokinetic effects of Tc 99m tilmanocept on resultant TUVs.

The second reason is to determine the longitudinal test re-test precision of TUV_{joint} and TUV_{global}. Identical image acquisitions performed 8 ± 1 days apart (e.g., planar WB scan at 60 ± 15 minutes compared with planar WB scan at 60 ± 15 minutes 8 ± 1 days after the first planar WB scan) will provide important information about the pharmacodynamic stability of Tc 99m tilmanocept as it relates to standardized TUV derivations. The overall purpose of these evaluations will be to determine if longitudinally repeated injection and imaging can provide

reliable quantitative data with minimal variation (assuming stable disease and treatment). The results from these assessments will have significant translational importance for the clinical utility of TUVs in the stable monitoring of changes in disease activity over time.

3.1.3 Arm 3: Change in anti-TNF α bDMARD Therapy (RA Subjects)

3.1.3.1 Description of Patient Population

This arm will be comprised of subjects with clinically diagnosed active RA who are candidates for initiation of, or change to, a new anti-TNF α bDMARD treatment. All subjects' RA diagnoses will be moderate to severe in accordance with a 2010 ACR/EULAR score of 6 or higher. All subjects receiving traditional DMARDs must have been on therapy for \geq 90 days and at a stable dose for \geq 30 days prior to the first imaging visit; all subjects receiving bDMARDs or JAK inhibitors must have been on stable therapy for at least 180 days prior to the first imaging visit; and all subjects receiving NSAIDs and/or oral corticosteroids must have been on therapy for at least 28 days prior to the first imaging visit. Upon completion of the first set of imaging assessments, all subjects will begin their new anti-TNF α bDMARD therapeutic regimen.

3.1.3.2 Overview of Study Procedures

Subjects in this arm will have a total of 5 on-site visits and 4 telephone safety assessments. The maximum possible study duration for these subjects will be 213 days.

Refer to [Section 7.1](#) for a detailed description of all study procedures. Refer to [Appendix 2](#) for a schedule of events and [Appendix 4](#) for a sequential diagram of study procedures.

3.1.3.3 Justification for Population

There are 2 reasons for the inclusion of this study population. The first is to determine the sensitivity of TUV_{global} towards the detection of anti-TNF α bDMARD therapy-driven changes in CD206 macrophage activity after 5 ± 1 weeks of treatment. By establishing that TUV_{global} has sufficient sensitivity to detect such changes, the predictive utility of this metric for downstream clinical outcomes can be further investigated.

The second reason, which is strongly predicated on the results of the first reason, is to establish a preliminary understanding of how changes from baseline of TUV_{global} to 5 ± 1 weeks of a new anti-TNF α bDMARD treatment correlate with changes in clinical response parameters. Refer to [Section 8.3](#) for an overview of all clinical parameters under investigation.

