- Temporal (1-hour and 3-hour) acquisitions—for the assessment of TUV stability across a 2-hour time window that is conducive to variable patient workflow in clinical practice (*Study Arms 1 and 2*), and;
- Longitudinal (8 \pm 1-day) acquisitions—for the assessment of TUV precision in the context of disease-specific Tc 99m tilmanocept pharmacodynamics (*Study Arm 2 only*).

The third arm is designed to assess the efficacy of TUV_{global} in clinically diagnosed subjects with active RA who are candidates for initiation of, or change to, a new anti-TNF α bDMARD therapy. Specific evaluations will include:

- *Sensitivity*—the capacity for TUV_{global} to detect changes in disease activity from baseline to 5 ± 1 weeks of new anti-TNF α bDMARD treatment (Δ TUV_{global[5w]}), and;
- *Clinical concordance*—the correlation between the change in TUV_{global} from baseline to 5 ± 1 weeks post-therapy and change in established rheumatological measures of disease response from baseline to 12 ± 1 and 24 ± 1 weeks post-therapy including Clinical Disease Activity Index (Δ CDAI_{12/24w}) and ACR Response (ACR_{12/24w}).

Methodology:

Study Arm 1: HC Subjects Free of Inflammatory Disease

Visit 1 (Screening; Day -30 to Day -1)

- Informed consent
- Review of study eligibility
- Collection of medical history (including medications)
- Vital sign assessment
- Physical examination (including height and weight)
- Clinical labs
- RA-specific labs
- Urinalysis
- Urine pregnancy test for subjects of childbearing potential
- 2010 ACR/ EULAR score

Visit 2 (Tc 99m Tilmanocept Administration and Imaging; Day 0)

Pre-Tc 99m Tilmanocept Administration

- Urine pregnancy test for women of child-bearing potential
- Electrocardiogram (ECG) up to 30 minutes prior to drug administration
- Post-ECG vital sign assessment
- Review of concomitant medications
- AE assessment

Tc 99m Tilmanocept Administration: Subjects will receive a single intravenous (IV) dose of 150 mcg tilmanocept radiolabeled with 10 mCi (370 MBq) of Tc 99m.

0-30 Minutes Post-Tc 99m Tilmanocept Administration

- ECG
- Post-ECG vital sign assessment

- AE assessment

60 ± 15 Minutes Post-Tc 99m Tilmanocept Administration

- AE assessment
- Image acquisition (in the following order)
 1. Planar scan of the whole body followed by up to a 15-minute *pause* (includes patient preparation for the subsequent acquisition);

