1.1 Design and Treatment

Subjects will receive the administration of Tc 99m tilmanocept through an IV route of administration. All subjects will receive a 150 µg mass dose of tilmanocept labeled with 10 mCi of Tc 99m in a 3 ml volume. Following injection a 10 ml sterile normal saline flush will be administered. The preferred site of IV placement will be between the elbow and wrist.

Arm 1 HC subjects receive a single administration of 10 mCi of Tc 99m in a 150 µg mass dose of tilmanocept. Arm 2 RA subjects receive two (2) IV administrations of 10 mCi Tc 99m in a 150 µg mass dose of tilmanocept. Arm 3 RA subjects receive up to four (4) administrations of 10 mCi Tc 99m in a 150 µg mass dose of tilmanocept.

Table 1 Study arms

Arm	Subjects	Evaluations
1	HC subjects clinically free of any inflammatory disease and/or joint pain.	Image, Re-image
2	Subjects with clinically diagnosed RA who have been on stable anti-rheumatic therapy.	Image, Re-image Test, Re-test
3	Subjects with clinically diagnosed RA who are candidates for initiation of, or change to, a new anti-TNF α bDMARD treatment.	Positive Predictive Value, Negative Predictive Value, Clinical Concordance

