The Kendall rank correlation between $\Delta TUV_{global[5w]}$ with $\Delta CDAL_{12w}$ and $\Delta CDAL_{24w}$ will be computed and a 95% confidence interval for its value will be computed using Fisher's Z-transformation. Similarly, the Kendall rank correlation between $\Delta TUV_{global[5w]}$ with changes from baseline in DAS28 and in each of the ACR Response Criteria components at weeks 12 and 24 will be computed and a 95% confidence interval for its value will be computed using Fisher's Z-transformation. The marginal distributions of the variables will be characterized with the mean, standard deviation, and the number of data pairs.

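### Sensitivity of TUV_global to change at Week 5 is the first reason for Arm 3, but no planned final analysis tests or bounds that change or sets it against Arm 2's 8-day repeatability

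*Protocol*

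**What the plan says.** The protocol states the sensitivity question in several places. The Synopsis (Study Design) defines it for Arm 3 as "the capacity for TUV_{global} to detect changes in disease activity from baseline to 5 ± 1 weeks" of the new treatment, and protocol Table 4 lists Sensitivity beside Clinical Concordance as an Arm 3 evaluation. Section 3.1.3.3 gives two reasons for the arm. "The first is to determine the sensitivity of TUV_{global} towards the detection of anti-TNF α bDMARD therapy-driven changes in CD206 macrophage activity" after 5 weeks. The section adds that, once the metric is shown to be one that "has sufficient sensitivity to detect such changes, the predictive utility of this metric for downstream clinical outcomes can be further investigated". The second is the correlation with clinical response, "which is strongly predicated on the results of the first reason".

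The formal objective for this arm in protocol 2.1 is narrower: "To assess the correlation of TUV and changes in TUV with changes in clinical assessments at multiple time points". The analyses follow the objective. SAP 4.2.1 plans Kendall correlations of the 5-week change with later clinical change, and for each "a 95% confidence interval for its value will be computed using Fisher's Z-transformation". For the change itself it offers only this: "The marginal distributions of the variables will be characterized with the mean, standard deviation, and the number of data pairs". SAP 4.2.2 adds further correlations, descriptive summaries, and PPV, NPV and overall accuracy for seven prediction algorithms, of which 1 to 6 use a fall of at least 10% in TUV_global. SAP Table 1 lists the Arm 3 evaluations as "Positive Predictive Value, Negative Predictive Value, Clinical Concordance", so Sensitivity no longer appears.

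Arm 2 is imaged twice, 8 days apart, on stable therapy. SAP 4.2.1 plans an RMSD with intervals for TUV_global at 60 minutes, and an exact binomial test that more than 80% of absolute changes are below 7.5%.

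**The concern.** If the plan is followed as written, the final report will reach no conclusion on the question that the protocol puts first and on which it rests the correlation aim. The planned analyses do not stand in for it. A rank correlation can be clearly non-zero when the average change is zero, and near zero when every subject improves by a similar amount. PPV and NPV describe agreement with clinical outcome, not whether the metric moved by more than its own measurement error.

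The benchmark for measurement error is collected in Arm 2, on the same metric and at the same 60-minute time point, but is never applied to Arm 3. At stake is how a reader should take a 10% fall at Week 5: how often would an unchanged subject show one?

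**Working it through.** **Planned sample size.** Inputs (SAP 1.3): N = 29, rho = 0.70, 97.5% limit, 0.15, Fisher's Z. The limits are tanh(atanh(0.70) ± 1.96/√26) = 0.449 and 0.849. The distance from rho to the upper limit is 0.149 at N = 29 and 0.151 at N = 28, so 29 reproduces on the upper-limit distance. The lower distance is 0.251. On either side, the size was set by precision of a correlation and not by detection of a change.

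**What each planned Arm 3 output says about the 5-week change.**

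| Output | Bears on sensitivity? |
|---|---|
| Kendall correlations with CI (protocol 9.5.3.3, SAP 4.2.1) | No; association only |
| Mean, SD and n of the change, per reader (Table 19 shell) | Descriptive; no interval or test |
| Plots by responder status (Figures 1-5) | Descriptive |
| PPV, NPV, accuracy (SAP 4.2.2) | No; agreement with clinical outcome |
| Interim analysis 3 (SAP 2.4) | Estimated the distribution of effects on TUV after 15 subjects reached Visit 4, and also served to optimize the metric |

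**How often would an unchanged subject show a 10% fall?** The documents give no SD for percent change in TUV_global. Assumptions: changes are normal with mean zero, the 7.5% criterion is on the percent scale, and 5-week noise equals 8-day noise. SAP 4.2.2 rounds to whole percent before applying the cut-off, so a call requires a change of about −9.5% or lower.

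If a fraction π lies within 7.5%, SD = 7.5 / z((1+π)/2), and the call rate is Φ(−9.5/SD).

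- *Arm 2 at the null boundary, π = 0.80.* SD = 7.5/1.2816 = 5.85. Call rate Φ(−1.62) = 5.2%. Two-sided 95% limit 1.96 × 5.85 = ±11.5%; one-sided 95% limit 1.645 × 5.85 = 9.6%.
- *Arm 2 just passing.* No alpha is stated; take one-sided 5%. With n = 38 under π = 0.80, P(X ≥ 35) = 0.039 and P(X ≥ 34) = 0.099, so 35/38 is needed. Then SD = 7.5/1.757 = 4.27, the two-sided limit is ±8.4%, and the call rate is Φ(−2.23) = 1.3%. At one-sided 2.5% (36/38), SD = 3.87, the limit is ±7.6% and the call rate is 0.7%.
- *Assumed SD of 10% or 20%.* Call rates are Φ(−0.95) = 17.1% and Φ(−0.475) = 31.7%. The matching fractions within 7.5% are 2Φ(0.75) − 1 = 55% and 2Φ(0.375) − 1 = 29%, far below 80%.

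**Is the missing analysis feasible?** With n = 29 and a two-sided 0.05 one-sample t-test, 80% power is reached at a mean change of 0.54 SD. The 95% CI half-width is 2.048 × SD/√29 = 0.38 SD. At an assumed SD of 10 or 20 points, the detectable mean change is 5.4 or 10.8 points and the half-width 3.8 or 7.6 points.

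**The case against.** The strongest reply is that the plan already supplies the pieces. Table 19 gives n, mean and SD per reader, from which a 95% CI against zero follows by arithmetic. Arm 2 gives RMSD with two intervals, percentiles of absolute difference and the fraction within 7.5%. Interim analysis 3 ran under its own approved plan, which is not among these documents and may have compared the change with zero or with Arm 2. Sensitivity is also not a listed objective or endpoint.

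Much of this stands. A reader might infer that the trial cannot answer its sensitivity question; the documents do not support that, because the gap is in the analysis plan and not in the data. What the reply does not supply is pre-specified inference in the final analysis or any link between the two arms. An interim look at 15 subjects that was also used to tune the metric is no replacement for the full arm.

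A reader might also infer that the 10% cut-off lies inside test-retest noise. That rests on two choices. It treats π = 0.80 as Arm 2's target, when it is the edge of the null hypothesis that the trial hopes to reject. It also applies a two-sided limit to a one-sided rule: even at that boundary the one-sided limit is 9.6%, below 10%. If Arm 2 passes, the cut-off lies outside the two-sided limit as well. The 17% to 32% figures rest on SDs with no source in the documents, in a range where planned Table 9 would already show Arm 2 failing.

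Nor are the improvement calls uninterpretable without this comparison. They are checked against ACR, CDAI, DAS28 and HAQ-DI with exact intervals, and heavy noise should appear there as poor predictive values.

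Finally, an Arm 2 comparison has limits: the arms are not randomized, 8 days is not 5 weeks, and SAP 2.5 defines change as a simple difference in Arms 1 and 2 but as a percentage in Arm 3.

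**Conclusion.** The point holds as a gap in the analysis plan. The protocol names sensitivity to 5-week change as an Arm 3 evaluation and the first reason for the arm. No planned final analysis tests that change, gives an interval for it, or relates it or the 10% cut-off to Arm 2 repeatability.

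The consequence for the cut-off depends on an SD that the documents do not give: about 5% of unchanged subjects would show a qualifying fall at the Arm 2 null boundary, about 1% if Arm 2 just passes, and 17% to 32% at an assumed SD of 10% to 20%, where Arm 2 would fail. These figures rest on the normal, zero-mean model. TUV_global is a sum over joints above a normal limit, so actual percent changes may be skewed. The rates apply directly to algorithms 2 and 5; algorithms 1, 3, 4 and 6 also use baseline TUV_global, and 3 and 6 use ACPA.

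The change should be made because it lets the trial answer its own first question with data in hand. Even then, attribution of any change to therapy would remain limited without a concurrent control.

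**What to change.** Add to SAP 4.2.1 for Arm 3, separately for each reader:

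- (a) Mean and median percent change in TUV_global from baseline to Week 5, each with a 95% CI, and a signed-rank test.
- (b) The Arm 2 8-day change in TUV_global at 60 minutes, computed on the same percent scale, with its 95% repeatability limits.
- (c) The fraction of each arm falling by 10% or more, and the fraction falling beyond the Arm 2 lower limit, with exact CIs.

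State that the between-arm comparison is descriptive, because the arms are not randomized and the intervals differ (8 days against 5 weeks). Restore Sensitivity to SAP Table 1, or explain there why it was replaced.

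Cost: a few extra tables, by reader and for the ITD and PP populations. No new visits, images or subjects are needed.
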